#### 5.4 Possible Risks Associated with Study Procedures

The only study-related procedure that could impact subject safety is in the collection of a direct anterior nares (nasal) swab. The risks of collecting a nasal nares swab may include symptoms associated with standard collection practices such as slight pain and/or minor bleeding.

Information collected for this study is confidential. Subjects will be identified using a study specific number at the time of enrollment. All study forms will be labeled with the study number. No identifiable patient information will be provided to the sponsor. However, officials of the FDA or other regulatory agencies may research records during the ordinary course of conducting their functions. A sponsor representative may also inspect research records to make certain the study data is accurate. The investigator, institution, regulatory agencies, and the sponsor will protect the confidentiality of the records.

No medical decisions will be based on investigational assay results generated as part of the study.

# 6 REGULATORY AND ADMINISTRATIVE REQUIREMENTS

#### 6.1 Good Clinical Practice

The investigator will ensure that this study is conducted in full compliance with the principles of the "Declaration of Helsinki" (as amended in Edinburgh, Tokyo, Venice, Hong Kong, and South Africa), International Council for Harmonization of Technical Requirements for Pharmaceuticals for Human Use guidelines, or with the laws and regulations of the country in which the research is conducted, whichever affords the greater protection to the study subject. For studies conducted under a United States investigational new drug application, the investigator will ensure that the basic principles of "Good Clinical Practice (GCP)," as outlined in 21 CFR 312, subpart D, "Responsibilities of Sponsors and Investigators," 21 CFR, part 50, 1998, and 21 CFR, part 56, 1998, are adhered to. This study is also subject to and will be conducted in compliance

with 21 CFR, part 320, 1993, "Retention of Bioavailability and Bioequivalence Testing Samples."

#### 6.2 Responsibility of Investigator

The principal investigator is responsible for the proper conduct of the study at their site(s). The investigator will ensure that the study is conducted in compliance with the protocol, the Clinical Study Agreement, and applicable regulations in 45 CFR 46, and any other applicable regulatory requirements. These requirements include:

- Obtaining IRB approval for the study and related documents before study initiation enrolling subjects.
- Obtaining informed consent from each subject in accordance with 21 CFR Part 50, as applicable.
- Protecting the rights, safety, and welfare of subjects under their care.
- Reporting adverse events.
- Coordinating and providing reasonable medical care to subjects for an adverse event related to study participation.
- Reporting protocol deviations to the sponsor and IRB per IRB requirements.
- Maintaining traceability and secured storage of all test kits and study samples.
- Ensuring confidentiality of all study documents, procedures, and study samples.

#### 6.3 Sponsor Responsibility

The sponsor has the overall responsibility for the conduct of the study, including assurance that the study meets regulatory requirements as applicable.

The sponsor's study-related duties and functions may be transferred to a contract research organization (CRO).

#### 6.4 **Protocol Deviations**

A protocol deviation is a failure to comply with the requirements specified within the clinical study protocol or IRB requirements. Investigators are not allowed to deviate from the protocol except when a deviation is necessary to protect a subject's rights and well-being, or the scientific integrity of the study.

#### 6.5 Changes to Protocol

In the event the study protocol is amended, the monitor will provide the principal investigator with the protocol amendment(s) and a revised protocol.

Protocol amendments that affect the subjects' rights or safety must be submitted to and approved by the IRB.

#### 6.6 Reconciliation of Study Material, Supplies and Samples

The sponsor will supply sufficient quantities of study materials and supplies to enable the site to complete the study. The site will return all unused materials and supplies to the sponsor or will dispose of unused materials and supplies, according to provided instructions. The site is required to maintain the inventory of the materials provided and will document the reconciliation of these materials. If materials are disposed of at the study site, the investigator must provide the sponsor with a signed record of disposition.

# 7 STATISTICAL CONSIDERATIONS

Except where otherwise specified, the following general principles apply to the planned statistical analyses. All statistical analysis will be conducted using a current version 9.4 (or later) of SAS (SAS Institute Inc., Cary, NC), Excel version 2010 or later, or other widely accepted statistical or graphical software as required. Categorical variables (e.g., sex) will be summarized with frequency counts and percentages.

# 7.1 Usability Study and Risk Mitigation for User Errors

The results will be analyzed to confirm the proper use of the QRI and usability of the MGC Health COVID-19 & Flu A+B Home Multi Test. The usability of the MGC Health COVID-19 & Flu A+B Home Multi Test will be considered valid if:

- The mean score of the subjects' response scores in the questionnaire are  $\leq 3$  for those questions with a score response between 1 and 5.
- 80% of the critical steps were performed correctly based upon the observer's assessment.
- 80% of the interpretation of the sample image results were correct.

The subject questionnaires and observer notes will be used to modify the QRI, if necessary, and additional usability testing will be conducted if needed.

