# **11 SUBJECT QUESTIONNAIRE**

The following questionnaire will be presented to subjects after completion of the MGC Health COVID-19 & Flu A+B Home Multi Test.

Subject Questions

- 1. Overall, how easy or difficult was it to understand the instructions to conduct the test?
  - 1. Very easy to understand
  - 2. Fairly easy to understand
  - 3. Easy
  - 4. Fairly difficult to understand
  - 5. Very difficult to understand
- 2. How easy or difficult was it to open the test cassette package?
  - 1. Very easy
  - **2.** Fairly easy
  - 3. Easy
  - 4. Fairly difficult
  - 5. Very difficult
- **3.** How easy or difficult was it to remove the sealed film covering from the sample collection tube?
  - 1. Very easy
  - 2. Fairly easy
  - 3. Easy
  - 4. Fairly difficult
  - 5. Very difficult

- **4.** How easy or difficult was it to understand the instructions on how to collect the sample from your nose or from another person?
  - **1.** Very easy to understand
  - 2. Fairly easy to understand
  - 3. Easy
  - 4. Fairly difficult to understand
  - 5. Very difficult to understand
- 5. How easy or difficult was it to understand the instructions to swirl the swab in the collection tube?
  - 1. Very easy to understand
  - 2. Fairly easy to understand
  - 3. Easy
  - 4. Fairly difficult to understand
  - 5. Very difficult to understand
- 6. How easy or difficult was it to understand the instructions on how to lift the swab out of the liquid and squeeze the collection tube?
  - 1. Very easy
  - 2. Fairly easy
  - 3. Easy
  - 4. Fairly difficult
  - 5. Very difficult

- 7. How easy or difficult was it to insert the nozzle lid onto the sample collection tube?
  - 1. Very easy
  - 2. Fairly easy
  - 3. Easy
  - 4. Fairly difficult
  - 5. Very difficult
- **8.** How easy or difficult was it to understand the instructions to add the sample from the collection tube to the sample well of the test cassette?
  - **1.** Very easy to understand
  - 2. Fairly easy to understand
  - 3. Easy
  - 4. Fairly difficult to understand
  - 5. Very difficult to understand
- 9. How easy or difficult was it to add the 3 drops into the test cassette?
  - 1. Very easy
  - 2. Fairly easy
  - 3. Easy
  - **4.** Fairly difficult
  - 5. Very difficult

10. How easy or difficult was it to read the test results?

- 1. Very easy
- 2. Fairly easy
- 3. Easy
- 4. Fairly difficult
- 5. Very difficult

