- **11.** How easy or difficult was it to understand the instructions on how to interpret the results of the test?
  - **1.** Very easy to understand
  - 2. Fairly easy to understand
  - 3. Easy
  - 4. Fairly difficult to understand
  - 5. Very difficult to understand

Additional Comments:

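### The questionnaire codes Easy (3) as worse than Fairly easy (2), and Section 7.1 averages these codes against a cut-off of 3, so for users who answer by the word the label order alone can change a question's verdict (minor).

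*Combined protocol and SAP*

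**What the plan says.** Section 7.1 of the combined protocol and SAP sets three conditions for calling usability valid. The first is that "The mean score of the subjects' response scores in the questionnaire are" 3 or less "for those questions with a score response between 1 and 5". The other two are that "80% of the critical steps were performed correctly based upon the observer's assessment" and that "80% of the interpretation of the sample image results were correct". The section adds that "The subject questionnaires and observer notes will be used to modify the QRI, if necessary", with further usability testing if needed.

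Section 11 prints the same five codes for all 11 questions: 1 *Very easy*, 2 *Fairly easy*, 3 *Easy*, 4 *Fairly difficult*, 5 *Very difficult*. In questions 1, 4, 5, 8 and 11 four of the options carry the words *to understand* (for example "2. Fairly easy to understand"), while option 3 is the bare word *Easy*. There is no neutral option, and the documents do not explain the order.

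Section 7 says in general that categorical variables "will be summarized with frequency counts and percentages". The Study Synopsis requires at least 30 completed subjects, at least 15 testing themselves and at least 15 testing a child aged 2 to 13. It lists subject evaluation of the kit as the second primary endpoint.

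**The concern.** The scale is not consistent with itself. On the difficult side *Fairly* is a weakener: *Fairly difficult* (4) is a milder complaint than *Very difficult* (5). On the easy side the same word earns a better score than the unqualified one. A user who means that a step was plainly easy, and picks that word, scores 3. A user who means that it was only fairly easy scores 2.

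For one answer taken alone this does no harm, because 1 to 3 are all easy and 4 to 5 are difficult. It matters once the codes are averaged, since the mean then gives numerical weight to an order that the words do not support. The cut-off also equals the code for *Easy*, so a question on which users centre on that word sits exactly at the limit.

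A second point applies whatever the labels are. A mean lets good scores offset bad ones, within a question and between the two user groups, so a question can pass while many users report difficulty.

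This is the only criterion in Section 7.1 that rests on subject evaluation, and the questionnaires also inform whether the QRI is revised.

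**Working it through.** **Inputs.** Codes and labels come from Section 11, the cut-off (mean of 3 or less) from Section 7.1, and N = 30, made up of two groups of 15, from the Study Synopsis. The documents do not derive the cut-off, so there is no stated figure to reproduce.

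**Formula.** With n1 to n5 the counts of each answer to one question, the printed mean is (n1 + 2·n2 + 3·n3 + 4·n4 + 5·n5)/30. Exchanging codes 2 and 3, with the answers held fixed, changes the mean by (n2 − n3)/30.

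**Label order, single patterns** (possible patterns, not forecasts):

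| Answers | Printed codes | Codes 2 and 3 exchanged |
|---|---|---|
| 30 Easy | 90/30 = 3.00, pass | 60/30 = 2.00, pass |
| 29 Easy, 1 Fairly difficult | (87 + 4)/30 = 3.03, fail | (58 + 4)/30 = 2.07, pass |
| 15 Fairly easy, 15 Fairly difficult | (30 + 60)/30 = 3.00, pass | (45 + 60)/30 = 3.50, fail |
| 10 Very easy, 10 Fairly easy, 10 Easy | (10 + 20 + 30)/30 = 2.00, pass | (10 + 30 + 20)/30 = 2.00, pass |

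**Label order, all patterns.** There are 46,376 ways to spread 30 answers over five options. The exchange turns a fail into a pass in 3,569 of them, all with printed means from 3.03 to 3.67. It turns a pass into a fail in another 3,569, all with printed means from 2.07 to 3.00. Every reversal contains at least one difficult answer: if all answers are 1, 2 or 3, the mean cannot exceed 3 under either order. These are counts of possible patterns and say nothing about how likely each one is.

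**Chance of a reversal.** This is an exact multinomial calculation for one question with N = 30. The answer distributions are assumptions and do not come from the documents. Every user is taken to answer by the word alone.

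| Assumed % at 1/2/3/4/5 | Expected printed mean | Fail becomes pass | Pass becomes fail |
|---|---|---|---|
| 30/30/30/8/2 | 2.22 | 0.00002 | 0.00002 |
| 20/20/50/8/2 | 2.52 | 0.002 | below 0.0001 |
| 20/20/40/15/5 | 2.65 | 0.032 | 0.0006 |
| 10/15/55/15/5 | 2.90 | 0.245 | 0.0001 |
| 10/40/10/30/10 | 2.90 | 0.0004 | 0.526 |

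**Averaging, whatever the labels.** 10 *Very easy* and 20 *Fairly difficult*: (10 + 80)/30 = 3.00, a pass with two thirds of users reporting difficulty. One group of 15 all at 2 and the other all at 4: (30 + 60)/30 = 3.00, a pass although every user in one group reported difficulty.

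**The case against.** The strongest reply is that users may answer by position. The options are a numbered list running from *Very easy* to *Very difficult*, and a user who reads it as a ladder gives correctly ordered codes whatever the words say. This stands. The exchange describes only users who choose by the word, so with any positional answering the effect should be smaller than the tables show.

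The larger chances also come from assumed distributions whose mean is close to 3. With 10% difficult answers the chance is 0.002 or less in the two cases above, and the documents give no reason to expect answers near the cut-off. This stands too. What remains is that an acceptance rule is needed most when answers are mixed, and there it depends on an unclear order.

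The plan has other safeguards. Both 80% criteria must also be met, and the questionnaires themselves, with a free comment field, inform revision of the QRI. The general statement on counts and percentages in Section 7 could cover the five options. These limit the damage. They do not correct the scale, split results by user group, or tie the share of difficult answers to the decision on the QRI.

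A reader might infer that a bad question could vanish in an average over the whole questionnaire: one question rated 5 by everyone passes if the other ten average 2.8, since (5 + 10 × 2.8)/11 = 3.00. Section 7.1 does not exclude a pooled mean, but it reads most naturally as a mean per question, so the point does not rest on this.

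A reader might also conclude that the scale needs a neutral midpoint. It does not. If option 3 became neutral and the cut-off stayed at 3, then 30 neutral answers would pass at 3.00 although nobody called the step easy.

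**Conclusion.** The point holds as a minor one. The label order is inconsistent on all 11 questions, Section 7.1 averages it, and nothing in the documents explains or corrects it. For word-based answers this can reverse a question's verdict in either direction, by a shift of up to just under one scale point among the patterns that reverse (3.03 to 2.07).

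The conditions are narrow: at least one difficult answer, unequal use of options 2 and 3, and a printed mean between 2.07 and 3.67. If nearly all answers are 1 or 2 there is no effect. The chances of 0.03 to 0.53 are upper illustrations, resting on assumed distributions and purely word-based answering.

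A reader might infer that the questionnaire criterion is likely to give the wrong answer, or that a lenient pass would wrongly validate the test. The documents support neither: they contain no forecast of answers, and the two observer-recorded criteria must be met as well. The masking of difficulty by a mean is a separate weakness that correct label order would not cure.

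**What to change.** Before enrolment:

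1. In Section 11, exchange the wording of options 2 and 3 on all 11 questions, giving 1 *Very easy*, 2 *Easy*, 3 *Fairly easy*, 4 *Fairly difficult*, 5 *Very difficult*. In questions 1, 4, 5, 8 and 11, put *to understand* on every option. Codes 1 to 3 stay on the easy side, so the cut-off of 3 keeps its meaning. Do not add a neutral midpoint unless the sponsor also reconsiders the cut-off.
2. In Section 7.1, add: *For each question, the number and percentage of subjects answering 4 or 5 will be reported beside the mean, overall and separately for self-testers and adults testing a child, and will be used when deciding whether to revise the QRI.*

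Item 2 addresses the averaging point. It does not depend on the order of options 2 and 3, so it still works if the printed form is already in use. Stating in Section 7.1 that the mean is taken for each question separately would be a useful clarification, and no more than that.

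The cost is IRB review of the reworded questionnaire, which Section 1.7 already sends to the IRB before enrolment, and one extra table. No subjects, visits, procedures or pass thresholds are added.

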# **Study Synopsis**

Title	MGC Health COVID-19 & Flu A+B Home Multi Test Usability Study
Protocol Number	MGC-1001
Protocol Date	16 January 2023
Protocol Version	1.0
Study Sponsor	Medical Group Care
Study Purpose	The purpose of this study is to evaluate the usability of the MGC Health COVID-19 & Flu A+B Home Multi Test in home use.
Investigational Material/Product	The MGC Health COVID-19 & Flu A+B Home Multi Test is a lateral flow immunochromatographic antibody assay intended for the simultaneous qualitative detection and differentiation of the nucleocapsid antigen from SARS-CoV-2, influenza A and/or influenza B directly from anterior nasal swab specimens obtained from individuals, who are suspected of respiratory viral infection within five (5) days of symptom onset. This test is intended for non-prescription home use with self- collected direct anterior nares swab samples from individuals ages 14 years and older or adult lay user collected anterior nares swab samples from individuals aged 2 to 13 years.
Study Objective	The objective of the study is to determine the usability of the MGC Health COVID-19 & Flu A+B Home Multi Test in a simulated home use environment.
Study Design	This is an open label study to evaluate the usability of the MGC Health COVID-19 & Flu A+B Home Multi Test using information from the Quick Reference Instructions (QRI).
Inclusion Criteria	
 
Subjects are eligible for inclusion if the following criteria are met:         
 
An Institutional Review Board (IRB) approved informed consent / assent, if applicable, is signed and dated prior to any study related activities.
 
Male and female subjects 2 years of age and older.
 
Subject is willing to provide a self-collected nasal swab sample. (If the subject is under the age of 14, an adult lay user will collect the sample.)
 
Subject agrees to complete all aspects of the study.
 
 
 

Exclusion Criteria	
 
A subject is not eligible for inclusion if any of the following criteria apply:
 
1. Subject has a visual impairment that cannot be restored with glasses or contact lenses.
 
2. Subject has prior medical or laboratory training.
 
3. Subject uses home diagnostics, e.g., glucose meters, HIV tests.
 
4. Subject has prior knowledge of their current COVID-19 or flu infection status.
 

Target	A minimum of 30 completed subjects with a minimum of 15 subjects	

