Population /	testing themselves and a minimum of 15 subjects testing another person	
Sample Size	(child 2 to 13 years old).	
Site	1 testing site in the United States	
Requirements		
Study Duration	The overall study duration is expected to be less than one (1) month, with	
Study Duration	subject participation completed in one visit of approximately one hour.	
	Primary Endpoints	
	1. Assess the usability of the Quick Reference Instructions (QRI)	
Study Endpoints	based upon observer evaluation.	
	2. Assess the usability of the kit for home use based upon subject	
	evaluation.	

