# 2 STUDY ENROLLMENT AND WITHDRAWAL

## 2.1 Study Population

Enrollment must include 15 subjects ages 14 and older, and 15 subjects ages 2-13 who present to the office location for COVID-19 and/or flu testing. The intent is to enroll subjects with varying educational levels and socioeconomic backgrounds.

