#### 3.5 Test Procedure

The observer will provide the subject the MGC Health COVID-19 & Flu A+B Home Multi Test and the QRI. The lot number and expiration date of the kit will be recorded. The observer will ask the subject to conduct the test. The subject will be expected to collect the sample, conduct the test, read and interpret the test result.

The observer will complete an observation form that will assess how well the subject followed the QRI to perform the critical steps for the test and interpret the test result.

The critical steps that each subject should perform accurately are as follows:

- Swab each nostril, rotating swab against nostril at least 5 times.
- Rotate the nasal swab in the sample collection tube liquid at least 5 times.
- Lift the swab out of the liquid in the collection tube and squeeze the tube against the swab tip 3 times.
- Squeeze the sample collection tube while removing the nasal swab.
- Press the nozzle lid firmly onto the sample collection tube.
- Transfer 3 drops from the sample collection tube into the sample well of test cassette.
- Do not move or lift the test cassette.
- Read the results between 15 and 20 minutes.

The subjects will interpret the test result and the observer will assess whether they agree or do not agree with the reading of the result. If they do not agree, they will provide the reason.

The observer will label each cartridge with the subject ID, protocol number, and date and will take a photograph of each test cartridge immediately after the subject has interpreted the result. Each photograph will be saved as an image titled with the subject's ID number.

After completion of the test process, the subject will complete a questionnaire on the clarity of the instructions provided, ease of performing the test, and ease of reading and interpreting their results.

The subjects will then be presented with 10 sample images of test results (1 negative, 7 positive, and 2 invalid) to confirm their ability to use the QRI to read and interpret all possible test results. The provided images will be as follows:

Image 1 - invalid test (no lines);

Image 2 – positive Flu A

Image 3 – positive COVID-19, Flu A, and Flu B

Image 4 – invalid test (Flu A line, no C line)

Image 5 – positive Flu B

Image 6 – positive Flu A, and Flu B

Image 7 - negative

Image 8 – positive COVID-19 and Flu A

Image 9 - positive COVID-19 and Flu B

Image 10 – positive COVID-19

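### Section 7.1 gives one kit-level 80% verdict without naming a user group, so read naturally one of the two recruited groups can clearly miss 80% while the step criterion is met

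*Combined protocol and SAP*

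**What the plan says.** The Study Synopsis sets the sample size by type of user: "A minimum of 30 completed subjects with a minimum of 15 subjects" "testing themselves and a minimum of 15 subjects testing another person", the other person being a child of 2 to 13 years. Section 2.1 repeats the split by age: "Enrollment must include 15 subjects ages 14 and older, and 15 subjects ages 2-13". The intended use in section 1.5.1 covers both self-collection from age 14 and collection by an adult lay user for ages 2 to 13.

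Section 7.1 then gives one verdict for the kit on three criteria. The first is a mean questionnaire score. The other two are "80% of the critical steps were performed correctly based upon the observer's assessment" and "80% of the interpretation of the sample image results were correct". Neither percentage is tied to a user group, and neither says whether the unit is the step, the user or the group. No interval is mentioned. The general principles in section 7 add only this: "Categorical variables (e.g., sex) will be summarized with frequency counts and percentages". No other section supplies a by-group rule or a confidence interval.

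**The concern.** The design treats self-testing and testing a child as two uses that each need their own minimum number of users. The decision rule does not carry that distinction through. If all steps from all users go into one percentage, strong results in one group offset weak results in the other. The kit could then meet the step criterion while one claimed user group falls clearly short of the plan's own threshold. Section 1.9 describes the critical steps as those that can make a result inaccurate if done wrongly, so a shortfall in one group bears directly on that group's use of the test.

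A second matter is that a group total can hide failure of a single step, including the swabbing step, which is the one that most obviously differs between the two uses.

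**Working it through.** **Inputs.** At least 15 users per group and 30 in total (Study Synopsis; section 2.1). Eight critical steps, counted from the list in section 3.5 that opens "The critical steps that each subject should perform accurately are as follows". Ten images per user, "10 sample images of test results (1 negative, 7 positive, and 2 invalid" (section 3.5). Threshold 80% (section 7.1). The plan gives no alpha, power, expected rate or precision target, so it has no figure of its own to reproduce. The true rates and within-user correlations below are assumptions.

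**Pass marks at the minimum size, all users pooled.**
- Steps: 30 × 8 = 240; 0.80 × 240 = 192.
- Images: 30 × 10 = 300; 0.80 × 300 = 240.
- Per group: 15 × 8 = 120 steps, pass mark 96; 15 × 10 = 150 images, pass mark 120.

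**How low one group can go.** With equal groups, a pooled 80% allows the weaker group to be at 2 × 80% minus the other group's rate. The exact (Clopper-Pearson) 95% intervals treat steps as independent.

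| Stronger group | Weaker group | Pooled | Weaker group, exact 95% CI |
|---|---|---|---|
| 108/120 (90%) | 84/120 (70%) | 192/240 | 61.0% to 78.0% |
| 114/120 (95%) | 78/120 (65%) | 192/240 | 55.8% to 73.5% |
| 120/120 (100%) | 72/120 (60%) | 192/240 | 50.7% to 68.8% |

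All three intervals lie wholly below 80%. Steps by the same user are likely to be correlated, which widens them. At a correlation of 0.2 the design effect is 1 + 7 × 0.2 = 2.4 and the effective number of steps is 120/2.4 = 50. The Wilson interval at 65% is then about 51% to 77%, still below 80%.

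**How often this would happen.** Simulation with 15 users × 8 steps per group, binomial for independent steps and beta-binomial for correlated steps. Assumed true rates are 95% in one group and 70% in the other.

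| | Independent | Correlation 0.2 |
|---|---|---|
| Pooled steps ≥ 192/240 | 88% | 78% |
| Weaker group ≥ 96/120 | 1% | 7% |

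**What a by-group rule costs a kit that performs equally in both groups.**

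| True rate, both groups | Correlation | Pooled rule met | Both groups ≥ 80% |
|---|---|---|---|
| 85% | 0 | 99% | 90% |
| 85% | 0.2 | 92% | 73% |
| 90% | 0 | >99% | >99% |
| 90% | 0.2 | >99% | 97% |

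**What a by-group total still misses.** Suppose every adult testing a child fails the swabbing step and performs the other seven at 95%. The group's score is (0 + 7 × 0.95)/8 = 6.65/8 = 83%, above 80%. With the other seven perfect it is 7/8 = 87.5%.

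**Precision of a bare pass.** The exact 95% interval for 192/240 is 74.4% to 84.9% with independent steps. The normal-approximation half-width, 1.96 × √(0.16 × (1 + 7 × ICC)/240), where ICC is the within-user correlation, is 5.1 points at 0 and 8.9 points at 0.3.

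**The case against.** **Pooling is not stated.** A reader might infer that the plan prescribes a pooled estimate. It does not: section 7.1 is silent on aggregation. Pooling is the natural reading of a single kit-level verdict that names no group. If the sponsor meant something else, the section needs to say so.

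**The pass probabilities are not the chance that the kit is declared valid.** Section 7.1 lists three criteria, naturally read as joint. The 88% and 78% concern the step criterion alone, and the overall chance cannot be higher.

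**The study has other safeguards.** A reader might conclude that child use would be supported on data showing the opposite. The documents do not go that far. Sections 1.9 and 7.1 allow the instructions to be revised and testing repeated, and the ages recorded under section 3.4 make a breakdown possible. But revision is discretionary and tied to no group result, and no breakdown is planned.

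**Most steps are the same in both groups.** Seven of the eight concern the tube, lid, drops, cassette and reading time. A gap as wide as 95% against 65% therefore needs failures beyond swabbing, and a by-group total alone would not catch failure confined to swabbing. This stands, and it is why a by-step table is needed as well.

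**The images involve no different task.** Both groups read the same ten. This also stands, so the case there is weaker.

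**An interval changes no decision.** Correct while the rule remains a comparison of the observed percentage with 80%. The interval only informs the reader.

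**Conclusion.** The point holds for the critical steps. On the natural reading of section 7.1, a split of 95% and 65% between the two groups meets the step criterion at the minimum sample size, while the weaker group's interval lies wholly below 80%. That result needs only the plan's own counts and threshold, equal groups and the pooled reading. How often it would arise depends on assumed true rates and correlation. For images the by-group result is a consistency check, since the documents give no reason to expect a gap. The documents do not support saying that the kit would be declared valid with these probabilities, or that the 80% threshold is wrong. The change should be made, but it does not call the study design into question.

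**What to change.** In section 7.1:

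1. State that the percentages for critical steps and for images are computed separately for self-testers and for adults testing a child, and that usability is called valid for a user group only if that group's own percentage is at least 80%. The threshold stays as it is.
2. Tabulate each of the eight critical steps by group, as users correct out of users observed.
3. Beside each percentage show a 95% interval with the user as the unit, for information only: a bootstrap that resamples users for the percentage of steps or images, and an exact binomial interval for each single-step count.

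The cost is a few lines of text and some tabulation, with no added subjects, visits or forms. The price is a stricter rule. At a true 85% in both groups, the chance of meeting the step criterion falls from about 99% to 90% with independent steps, and from 92% to 73% at correlation 0.2. At a true 90% it remains about 97% even at that correlation. Intervals will be wide with 15 users per group: 12 of 15 correct on one step has an exact 95% interval of 51.9% to 95.7%. Requiring the lower limit to reach 80% would be far stricter (at least 105/120 steps per group even if independent) and is not proposed.
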